4.1.4 Level of significance

All statistical test will be performed with a two-tailed alpha (α) of 0.10, all confidence intervals which will be calculated will be 95% confidence intervals.

Test results p<0.05 will be regarded as 'significant', test results with p-values p<0.10 as 'remarkable' or as 'trends / tendencies'.

4.1.5 Interim analysis

An interim analysis is planned when all patients have completed the follow-up visit V07 (day 180), an additional evaluation of safety and performance of ARGOS-SC implant is to be carried out after all patients have undergone the follow-up visit V06 (day 90). (Addendum I to Clinical Investigation Plan ARGOS-SC).

4.1.6 Equivalence / Non-inferiority study

Not applicable.

4.1.7 Subgroup analysis

In order to permit investigation of their impact on performance and safety, information will be collected prospectively on the following variables:

- Gender
- Medical History (primary underlying ophthalmic illness or injury necessitating the non-penetrating glaucoma surgery)
- Pre-treatment
- Concomitant medications
- Post-surgical complications
- Successful implantation
- Age groups
- Country of investigational site
- Educational level

Which subgroup analyses are actually performed will be decided at a final data review meeting preceding the statistical analysis, based on the actual distribution of subjects in the study population.

4.2 Definition of baseline and endpoints, and derived variables

Baseline values are determined in the Screening visit before the implantation procedure.

Post values are defined as the values after the implantation procedure.

Change from baseline (Δ) is defined as the difference between the baseline value obtained before implantation procedure and the post value after implantation procedure separately for each visit:

 Δ = Post value - Baseline value

Percent change from baseline is defined as the change from baseline divided by the baseline value times 100%:

 $\%\Delta$ = ((Post value - Baseline value) / (Baseline value)) x 100

In case of measurements / assessments before (pre) and after (post) implantation the change from baseline and the percent change from baseline (if indicated) will be calculated.

In case of ordinal scales, shift tables (before vs. after) may be used instead of differences.

4.3 Disposition of patients

The number and percentage of screened, enrolled, implanted subjects and those who complete the follow-up will be tabulated for the safety set. The number of screening failures and early withdrawals will be tabulated with the reason for termination. The reasons for premature termination are classified as follows:

- Death
- Adverse events / Serious adverse events
- Lost to follow-up
- Voluntary withdrawal not for adverse event
- Other

4.4 Demographic data and other baseline characteristics

- Inclusion criteria
- Exclusion criteria
- Demographic data
- Educational level
- Medical history
- Glaucoma anamnesis
- Concomitant glaucoma medication at start of study
- Other Concomitant medication at start of study
- Pregnancy test (for female subjects of childbearing potential)

4.5 Surgery data

Surgery related data (study eye, examination prior surgery, ARGOS-SC implantation, Intraocular lens implantation, complications)

4.6 Analysis of endpoints

4.6.1 Performance endpoints

The evaluation uses the following methods to analyze the agreement between two different measurement methods

Bland-Altman Plot:

Bland and Altman introduced the Bland-Altman plot to describe agreement between two quantitative measurements by constructing limits of agreement. These statistical limits are calculated by using the mean and the standard deviation (s) of the differences between two measurements. To check the assumptions of normality of differences and other characteristics, they used a graphical approach.

The resulting graph is a scatter plot XY, in which the Y axis shows the difference between the two paired measurements (x-y) and the X axis represents the average of these measures ((x+y)/2). In other words, the difference of the two paired measurements is plotted against the mean of the two measurements. Bland-Altman recommended that 95% of the data points should lie within \pm 2s of the mean difference. This is the most common way to plot the Bland-Altman method.

The bias is computed as the value determined by one method minus the value determined by the other method. If one method is sometimes higher, and sometimes the other method is higher, the average of the differences will be close to zero. If it is not close to zero, this indicates that the two assay methods are systematically producing different results.

Concordance correlation coefficient

Concordance correlation coefficient (r_{ccc}) measures the agreement between two variables X and Y. Lawrence Lin has defined the form of the concordance correlation r_{ccc} as^[1]

$$r_{ccc} = 2 r s_x s_y / ((s_x^2 + s_y^2) + (m_x - m_y)^2)$$

with

 $r = s_{xy}/(s_x s_y)$ (Pearson correlation coefficient)

 m_x = mean of X

 $m_y = mean of Y$

 s_x = standard deviation of X

 s_y = standard deviation of Y

 s_{xy} = covariance of x and Y

The concordance correlation r_{ccc} has an range of -1 to 1. Values near +1 indicate strong concordance between x and y, values near -1 indicate strong discordance and values near zero indicate no concordance. There is no clear-cut agreement as to how to interpret the values, although one approach is to interpret Lin's r_{ccc} as for Pearson's correlation coefficient (e.g. values less than .20 are poor, while values greater than .80 are excellent).

The following values will be calculated:

- Calculation of the average of the (up to) 3 IOP measurements using GAT (GAT_{mean})
- Calculation of the average of the (up to) 3 IOP measurements using ARGOS-SC (ARGOS1_{mean})
- Calculation of the average of the (up to) 3 IOP measurements using DCT (DCT_{mean})
- Calculation of the average of the (up to) 3 IOP measurements using OPA (OPA_{mean})
- Calculation of the average of the (up to) 3 IOP measurements using ARGOS-SC (ARGOS2_{mean})
- Difference IOP_{d1}= ARGOS1_{mean} GAT_{mean}
- Mean IOP_{mean1} = (ARGOS1_{mean} + GAT_{mean})/2
- Difference IOP_{d2}= ARGOS2_{mean} DCT_{mean}
- Mean IOP_{mean2} = (ARGOS2_{mean} + GAT_{mean})/2

 $ARGOS1_{mean}$ / GAT_{mean} / IOP_{d1} (statistical parameters, concordance correlation coefficient r_{ccc} , Bland-Altman-Plot with IOP_{mean1} vs. IOP_{d1} , plot of $ARGOS1_{mean}$ vs. GAT_{mean}), separate for each visit

 $|IOP_{d1}| \leq 5 \text{ mmHg (N, \%)}$

ARGOS2_{mean} / DCT_{mean} / IOP_{d2} (statistical parameters)

 $|IOP_{d2}| \leq 5 \text{ mmHg (N, \%)}$

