4.9 Clinical experience with similar devices

4.9.1 Method validation: Clinical experience with EYEMATE-IO

In the ARGOS-02 clinical trial, which involved the EYEMATE-IO device, surgical complications were reported in 7 of 23 patients. In five of those seven patients, complications occurred during the implantation of the EYEMATE-IO device. The complications most often (five times each) were Irisprolapse/floppy iris and pigment dispersion. Flat anterior chamber and "vis a tergo" ("pressure from behind") were reported twice each.

Serious adverse events which were considered to be at least possibly related to either the implant or the implantation procedure were:

- Fibrin reaction in the anterior chamber (postoperative event which was resolved by medication)
- Increased intraocular pressure (was most likely caused by pigment dispersion)
- Corneal decompensation (was most likely caused by excessive surgical manipulation)

These complications are connected with the cataract surgical procedure and are possibly related to the implants position but not to the functional principle of the implant, and as such not associated with the ARGOS-SC device.

The EYEMATE-IO IOP measurement method showed an excellent level of concordance to the conventional GAT IOP measurement though a dependence of the differences between GAT IOP and EYEMATE-IO IOP on the respective IOP level was observed. In the range of physiological IOP (\leq 21 mmHg), the differences between both methods are in the range of the physiological variety of IOP. In IOPs considered to be higher as normal (> 21 mmHg) the differences between the two methods were higher than the average variety of IOP in human eyes. The higher the IOP the larger the differences between the methods, as also observed by other groups [26, 27].

Page 40 of 97

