9.1.4 Performance Analysis

The probability distribution of the difference of the paired measurements grouped within 1 mmHg will be compared to the primary objective of the accepted 70% of the measurements to agree between +/- 5 mmHg.

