2.9 Study endpoints

2.9.1 Primary endpoints

Performance:

Level of agreement between measurements made using GAT and the ARGOS-SC system at visit V02 - V09.

The concordance of the intraindividual measurement values of GAT and ARGOS-SC will be indicated by the concordance correlation coefficient r_{ccc} (4.6.1), separate for each visit

Additionally, the absolute difference between the GAT and ARGOS-SC measurement will be scaled in \leq 5mmHg and > 5 mmHg and the frequency distribution will be displayed (4.6.1, Table 2).

The Bland-Altman (mean-difference) plot and a X-Y plot should illustrate the comparison of the two methods (4.6.1, Figure 1).

The level of agreement between Pascal DCT and ARGOS-SC will be evaluated analogously.

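### No numeric agreement result uses IOP level, although the protocol reports that the predecessor sensor's differences from GAT grew with IOP

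*SAP*

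**What the plan says.** Protocol 4.9.1 summarises the predecessor (EYEMATE-IO) against GAT. Differences depended on IOP level. Above 21 mmHg, "the differences between the two methods were higher than the average variety of IOP in human eyes", and in general "The higher the IOP the larger the differences between the methods". No slope, SD or count is given.

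For ARGOS-SC against GAT, SAP 4.6.1 plans:
- limits of agreement: "These statistical limits are calculated by using the mean and the standard deviation (s) of the differences between two measurements";
- a Bland-Altman graph in which "the difference of the two paired measurements is plotted against the mean of the two measurements", an X-Y plot and a concordance correlation coefficient, "separate for each visit";
- a two-category share, in which "the absolute difference between the GAT and ARGOS-SC measurement will be scaled in" at most 5 and more than 5 mmHg. Mock-up Table 2 shows it by visit.

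The plots have an illustrative role: "The Bland-Altman (mean-difference) plot and a X-Y plot should illustrate the comparison of the two methods" (SAP 2.9.1). IOP level is not among the nine subgroup variables in Protocol 9.9 and SAP 4.1.7.

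The success target stands in the protocol, not the SAP. Under Protocol 9.1.4 the distribution of paired differences is "compared to the primary objective of the accepted 70% of the measurements to agree between +/- 5 mmHg". Protocol 9.5 repeats the 70% and adds a parenthesis saying that the GAT/ARGOS-SC limits of agreement lie within ±5 mmHg. Neither section sets a condition on IOP level.

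For DCT, SAP 2.9.1 promises an analogous evaluation. SAP 4.6.1, however, lists only statistical parameters and the ±5 mmHg share, and forms IOP_mean2 from ARGOS2_mean and GAT_mean.

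**The concern.** Limits built from one mean and one SD describe agreement well only if bias and spread are roughly constant over the measuring range. The protocol gives a reason to doubt this: it reports the opposite pattern for a sensor that, in its section 4.8.1.4, shares the technology of ARGOS-SC.

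The readings are taken after IOP-lowering surgery, so high values are likely to be a minority. A summary over all IOP levels is then dominated by low and normal readings. Yet Protocol 4.1 presents the detection of IOP peaks as a purpose of the device. At stake is whether the report can say, in numbers, how well the sensor agrees with tonometry where the protocol itself expects larger differences.

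**Working it through.** **1. The plan's own figure.** Protocol 9.2 asks for about 120 measurement pairs. It does not state the expected agreement, so 120 cannot be derived from the documents. With an assumed 80% against 70%, two-sided alpha 0.10 (SAP 4.1.4) and 80% power (Protocol 9.3):

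n = [(1.645·√(0.7·0.3) + 0.842·√(0.8·0.2)) / 0.10]² ≈ 119.

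This calculation treats all pairs as one pool and gives no weight to any IOP range.

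**2. What the 70% share requires at low IOP.** Let h be the share of pairs above 21 mmHg, and pL and pH the agreement at or below and above 21 mmHg. The overall share is P = (1−h)·pL + h·pH. Setting pH = 0 and P ≥ 0.70 gives pL ≥ 0.70/(1−h). The documents do not give h, so it is assumed. With 24 patients and 8 follow-up visits there are at most 24 × 8 = 192 visit-level pairs.

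| h (assumed) | pairs >21 of 192 | pL needed if none of them agree |
|---|---|---|
| 5% | about 10 | 0.70/0.95 = 74% |
| 10% | about 19 | 0.70/0.90 = 78% |
| 20% | about 38 | 0.70/0.80 = 87.5% |
| 25% | 48 | 0.70/0.75 = 93.3% |

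**3. What constant limits show.** Assume a low-range SD of 2.5 with no bias, a high-range bias of +8 with SD 5 mmHg, and h = 10%.
- Agreement within ±5 mmHg is 95.4% in the low range and 27.0% in the high range.
- Overall share: 0.9·0.954 + 0.1·0.270 = 88.6%.
- Mixture mean: 0.1·8 = 0.8. Variance: 0.9·(2.5² + 0.8²) + 0.1·(5² + 7.2²) = 13.9, so the SD is 3.73. Limits: 0.8 ± 1.96·3.73 = −6.5 to +8.1.
- High-range limits: 8 ± 1.96·5 = −1.8 to +17.8.

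A comfortable 88.6% thus coexists with poor agreement above 21 mmHg.

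**4. The two parts of Protocol 9.5.** With zero bias and normal differences, exactly 70% within ±5 mmHg means SD = 5/1.036 = 4.82, and limits of ±1.96·4.82 = ±9.46. Limits within ±5 mmHg need SD ≤ 5/1.96 = 2.55. These are different conditions. The example in step 3 passes the first and fails the second.

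**5. Illustration from mock-up Table 2 (not trial evidence).** The printed SDs determine the slope of difference on mean:

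cov = (SD_A² + SD_G² − SD_d²)/2; Var(mean) = (SD_A² + SD_G² + 2·cov)/4; slope = [(SD_A² − SD_G²)/2]/Var(mean).

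The same inputs reproduce the printed r_ccc values (0.91, 0.80, 0.76, 0.78, 0.68). For V06:
- cov = (6.60² + 4.10² − 4.39²)/2 = 20.55;
- Var(mean) = (60.37 + 41.10)/4 = 25.37;
- slope = 13.375/25.37 = 0.53.

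For V02 to V05 the slopes are 0.03, −0.18, 0.39 and 0.32. The shares within ±5 mmHg stay between 77.3% and 95.2% (89/101 = 88% overall). At V06 the highest ARGOS-SC value is 33 and the highest GAT value 19, so that pair differs by at least 14 mmHg. It must be the one pair beyond 5 mmHg, at a visit showing 94.1% agreement. None of the listed numeric outputs would report the slope.

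**The case against.** The strongest reply is that the plan already displays the pattern. A plot of difference against mean is the standard way to see an IOP-dependent difference, and an X-Y plot is added. The SAP also reports the SD, minimum and maximum of the differences, and everything is shown by visit. The study is exploratory, with 24 patients, and SAP 4.1.6 marks equivalence as not applicable. This stands against three stronger readings:

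- A reader might infer that the SAP reduces agreement to one pooled share, so that failure at high IOP would be invisible. It does not. The share is shown by visit, and for GAT the plots could reveal a trend. What is missing is a number. Splitting by visit does not supply it, because it does not separate high from low IOP.
- A reader might infer that the trial would pass whatever happened above 21 mmHg. That holds only if the 70% share alone decides, and only if low-range agreement is high enough: 93.3% when a quarter of pairs fail. The mock-up GAT quartiles cannot fix the size of the high range. They are dummy figures for V02 to V06 and refer to GAT, not mean IOP.
- A reader might infer that the predecessor's device error grew, so that constant limits must be too wide at low IOP and too narrow at high IOP. Protocol 4.9.1 reports differences between two methods and does not say whether bias or spread grew. Protocol 8.2.2 regards DCT as nearer true IOP than GAT at higher pressures, so GAT may contribute. Protocol 3.3 adds that the form and location of ARGOS-SC differ enough to need independent investigation.

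Two technical cautions also stand. A stratum above 21 mmHg may be very small: a normal approximation to the mock-up GAT values puts about 3% there, or roughly 6 of 192 pairs. And a slope of difference on mean arises whenever the two methods have unequal variances.

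**Conclusion.** The gap is real and should be closed. The protocol documents an IOP-dependent difference for the predecessor, yet no planned numeric result for ARGOS-SC uses IOP level. On the 70%-only reading, complete disagreement above 21 mmHg is compatible with success once low-range agreement reaches about 74%, 78% or 87.5%, for assumed high-range shares of 5%, 10% or 20%. The arithmetic is exact, but the high-range shares are assumptions. If the parenthesis in Protocol 9.5 imposes conventional limits within ±5 mmHg, the criterion is much stricter and the worked example fails it. The documents do not settle which reading applies. They also do not show that ARGOS-SC will behave like its predecessor, nor that a trend would escape the eye. The point is that it would be neither estimated nor reflected in the claim.

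**What to change.** Add to SAP 4.6.1, before database lock:

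1. A mixed-model regression of IOP_d1 on IOP_mean1 over all visits with a patient random effect, plus a regression of the absolute residuals on IOP_mean1. The first addresses a trend in bias, the second a change in spread. Report IOP-dependent limits of agreement if either changes with IOP.
2. The share within ±5 mmHg for mean IOP ≤21 and >21 mmHg, the cut used in Protocol 4.9.1. Present it descriptively, with counts of pairs and patients.
3. A statement that the agreement claim covers only the IOP range observed.

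Do the same for DCT, with IOP_mean2 formed from ARGOS2_mean and DCT_mean.

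The cost is a little more analysis work and no new data. The >21 mmHg stratum will be imprecise, which is why the regression should carry the main weight. Because the slope partly reflects unequal variances of the two methods, it should be read alongside the DCT comparison.

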8.3.12 Performance

IOP level will be assessed at every follow-up visit in a series of 2 GAT standard measurements followed by 3 consecutive measurements with the ARGOS-SC system. From V05 (day 30) on, if available, additional 2 DCT measurements followed by 3 consecutive measurements with the ARGOS-SC system. **Optional:** At visits V06, V07 and V09, 24-hours measurements with GAT and ARGOS-SC will be done inpatient.

Patients will be given a MESOGRAPH reading device at Visit 01 in order to measure the IOP daily at home. Measurements shall be taken at least 4 times per day (morning, noon, afternoon, evening). The MESOGRAPH reading device will be connected to an external GSM module, which will transfer the measured value directly to a secure database. Investigators can log into the database in order to track the pressure levels of their patients as required. At every follow-up visit, site staff will examine the subject's hand-held reader device and download all readings recorded since the last visit. In addition, they will ask subjects non-leading questions to determine if any device deficiencies occurred since the last visit. All device deficiencies will be recorded on the device deficiency page of the CRF.

To ensure accuracy and comparability of the recorded parameters, all responsible site personnel will be thoroughly instructed on the agreed measurement methods.

To access the user acceptance of the implantation procedure and the general usability of the ARGOS-SC system, surgeons and personnel performing the ARGOS-SC system measurements will be asked to complete user acceptance questionnaires. The aim of these questionnaires is to gain more information about the level of user-acceptance of the ARGOS-SC system during implantation and during IOP measurement. The data collected with these questionnaires is only of exploratory nature and will not be included in the analysis. Results will provide the sponsor with data that could influence future device system improvements.

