8.3.13.14 Intraocular pressure (IOP) measurement

Intraocular pressure will be measured using three techniques. Goldmann Applanation Tonometry (GAT) will be performed in the clinic at every visit and if available, Pascal Dynamic Contour Tonometry (DCT) at V05 through V09. ARGOS-SC measurements will be performed in the clinic at every visit and by the patient at home between the visits. Only GAT will be used to guide any treatment decisions. The GAT and DCT must be performed by as few dedicated investigators as possible at each site to reduce potential bias.

IOP measurement in the clinic

IOP measurement will be conducted at V02 through V09 as a series of 2x GAT (in case of a difference of more than 2mmHg, a third GAT-measurement is required) followed by 3x ARGOS-SC system. When series of measurements are made, GAT must always be used first to avoid potential operator bias. For the ARGOS-SC measurements the patient has to stay in the same position as for the GAT-measurements (chin on chin rest, forehead installed). From V05 through V09 additionally (if available), a series of 2x DCT (in case of a difference of more than 2mmHg, a third DCT-measurement is required)

followed by 3x ARGOS-SC will be performed after the series of GAT and ARGOS-SC measurements. For the ARGOS-SC measurements, the patient has to stay in the same position as for the DCT-measurements (chin on chin rest, forehead installed).

Optional: At V06, V07 and V09, the patient will be hospitalized for 24-hours measurements with GAT and ARGOS-SC. IOP measurements with ARGOS-SC will be done automatically via an external antenna. IOP measurements with GAT will be done every three hours, if it is possible even at night. If night measurements are not possible every three hours at night, the last measurement should take place between 22 and 24 o'clock and the three-hours rhythm should be resumed between 5 and 7 o'clock on the next morning.

ARGOS-SC system measurement by the subject at home

Subjects will receive detailed instruction in the use of the MESOGRAPH reading device. At V02, they will receive an individual MESOGRAPH reading device, a copy of the instructions for use and the Multiline Connector to perform self-tonometry at home. Subjects will be requested to perform at least 4 IOP measurements daily with the MESOGRAPH, one each in the morning after getting up, at noon, in the afternoon and in the evening before going to bed.

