9.2 Sample Size Calculation

The sample size calculation was based on the study's dual purpose of establishing safety and comparability of IOP measurements with the ARGOS-SC system to those made with GAT and DCT. IOP measurements will be made with all devices at various time points, resulting in a within individual control for IOP variables. Based on these calculations (performance, safety) and considering possible drop-outs, the exploratory investigation will enroll 24 patients. The minimum number of measurements required to hold the performance claim is approx. 120. With multiple (>8) measurements with either method (ARGOS, GAT) per patient, a sufficient number of paired measurements (in total >>120 measurement pairs) will be available to show equivalence of the methods (primary objective)[2].

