9.5 Pass/fail criteria to be applied to the results of the clinical investigation

This investigation will be considered a success if no more than one of the 24 patients experiencing SADEs during the follow-up period (SADEs evaluated by DSMB) and if 70% of the measurements agree between +/- 5 mmHg (limits of agreement from GAT and ARGOS-SC measurements are between +/- 5 mmHg).

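### SAP 4.6.1 reports limits of agreement and the share within 5 mmHg only for visit means of up to three ARGOS-SC readings, so neither figure describes the single reading a patient takes at home

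*SAP*

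**What the plan says.** **Success rule.** Protocol 9.5 requires that "70% of the measurements agree" to within ±5 mmHg, and adds in brackets that the "limits of agreement from GAT and ARGOS-SC measurements are between" those same bounds. Protocol 9.1.4 describes the analysis as "The probability distribution of the difference of the paired measurements grouped within 1 mmHg". Protocol 9.2 also counts in measurements and pairs: "With multiple (>8) measurements with either method (ARGOS, GAT) per patient". None of these sections mentions averaging.

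**Clinic data.** Protocol 8.3.12: "IOP level will be assessed at every follow-up visit in a series of 2 GAT standard measurements followed by 3 consecutive measurements" with ARGOS-SC. A third GAT reading is added when the first two differ by more than 2 mmHg (Protocol 8.3.13.14). SAP 2.8.1 allows two or three sensor readings.

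**Analysis.** SAP 4.6.1 specifies "Calculation of the average of the (up to) 3 IOP measurements using GAT" and "Calculation of the average of the (up to) 3 IOP measurements using ARGOS-SC". One difference per visit follows, and the Bland-Altman plot, the concordance coefficient and the count within 5 mmHg all use it. The DCT comparison also rests on means. The SAP does not restate the 70% rule or say that its unit is a visit mean.

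**Home use.** Protocol 8.3.13.14: "Subjects will be requested to perform at least 4 IOP measurements daily with the MESOGRAPH, one each in the morning after getting up", with the others at noon, in the afternoon and in the evening. SAP 4.6.3 leaves the home profiles out of the evaluation.

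**Repeatability.** It is a secondary endpoint (Protocol 8.1.3.2, SAP 2.9.2), but SAP 4.6.3 names no statistic for it, and it does not enter the limits or the share.

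**The concern.** The mean of three readings is less noisy than one reading. Limits of agreement and a within-5-mmHg share built from means therefore describe a three-reading average. The protocol's case for the device rests heavily on self-measurement at home (Protocol 3.3, 6.1, 6.7), where the unit is one reading. Because home readings are not evaluated, the clinic series is the only agreement evidence, and in it no reading is compared with GAT on its own.

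Two things are at stake. The first is whether the figures set against Protocol 9.5 use the unit that the rule was meant for; the SAP does not say. The second is that someone reading the report could apply the visit-mean limits to a single home value, for which they are too narrow.

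**Working it through.** **The plan's own figure.** Protocol 9.2 asks for about 120 measurements. With p0 = 0.70 (Protocol 9.5), two-sided alpha 0.10 (Protocol 9.3, SAP 4.1.4), power 80% and an assumed true share p1 = 0.80, the one-sample formula gives

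n = [(1.645·√(0.70·0.30) + 0.842·√(0.80·0.20)) / 0.10]² ≈ 118.9, so 119.

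This is a back-solved match, because p1 is not in the documents: p1 = 0.78 gives 190 and p1 = 0.82 gives 81. The count does not settle the unit. The plan yields 24 × 8 = 192 visit-level GAT pairs, or 576 single sensor readings, and both exceed 120.

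**Formula.** Let s be the SD of (mean of three ARGOS-SC readings − GAT mean) and w the sensor's within-series SD. With independent errors within a series, one reading carries variance w² where the mean carries w²/3. Hence

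SD(single)² = s² + (1 − 1/3)·w² = s² + (2/3)·w².

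Bias, drift and GAT error are the same in both. Limits = bias ± 1.96·SD. Under normality, share = Φ((5 − bias)/SD) − Φ((−5 − bias)/SD).

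**Assumed values of w (not given in the documents).**
- 0.67 mmHg: the 3-sigma accuracy of 2 mmHg in Protocol 4.8.1.4, divided by 3 and read entirely as random error.
- 1.11 to 1.79 mmHg: the smallest and largest SDs implied by the rabbit limits of agreement in Protocol 4.8.2.1. For example, −3.04 to 3.98 gives 7.02/2/1.96 = 1.79. These are total SDs that include between-eye spread, so 1.79 is a generous upper value.

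**Results at zero bias.**

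| Visit-mean result | s | w = 0.67 | w = 1.11 | w = 1.79 |
|---|---|---|---|---|
| Limits ±5.00 mmHg | 2.55 | ±5.11 | ±5.31 | ±5.76 |
| Share 72% | 4.63 | 71.7% | 71.1% | 69.7% |
| Share 75% | 4.35 | 74.6% | 74.0% | 72.4% |

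Worked cell: √(2.551² + (2/3)·1.79²) = √(6.508 + 2.136) = 2.940, and 1.96 × 2.940 = 5.76.

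**How near the boundary the result must be.**
- A zero-bias share of 70% corresponds to SD 4.824. Solving s² = 4.824² − (2/3)w² gives visit-mean shares of 70.3% (w = 0.67) and 72.3% (w = 1.79). Only a visit-mean share between 70% and that value falls below 70% for single readings.
- For the limits, √(25 − 1.96²·(2/3)w²) gives half-widths of 4.88 mmHg (w = 0.67) and 4.10 mmHg (w = 1.79). Only visit-mean limits between that value and 5.00 move outside ±5 mmHg.

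**Scale check on the mock-up.** With the placeholder biases and SDs of SAP Table 2 (SDs 2.16 to 4.39 mmHg), single readings widen the limits by 0.07 to 0.13 mmHg per side and lower the share by 0.3 to 0.5 points at w = 0.67. At w = 1.79 the figures are 0.46 to 0.88 mmHg and 2.3 to 3.7 points.

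**The case against.** **One pair per visit is a fair reading of the protocol.** The clinic measurement is defined as a series, and nothing pairs an individual sensor reading with an individual GAT reading. The 192 visit pairs exceed the stated 120. This stands: averaging repeats is normal in a method comparison and is not an error, and replacing the visit mean as the main unit would be a trade-off. What remains is that the SAP never states the unit for the Protocol 9.5 rule and gives no single-reading agreement.

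**Reading noise is covered by the repeatability endpoint.** Partly so. The endpoint exists, and SAP 2.9.2 also compares it with OPA. But no statistic is named, and nothing carries it into the limits or the share.

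**Home readings lie outside the primary objective.** True. They are set aside as not comparable with clinic readings (Protocol 9.11.2, SAP 3.7). That leaves the clinic series as the only source for a single-reading figure. The documents also do not say whether one displayed MESOGRAPH value is itself an average. If it is, w is simply the SD of the displayed values and the formula is unchanged.

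**A stronger reading is tempting.** A reader might take the ±5 mmHg imprecision of repeated IOP measurements in Protocol 3.2 as a sensor SD near 2.5 mmHg and infer that averaging by itself carries the share across 70%. That passage concerns repeated tonometry and treatment-effect detection, not directly consecutive sensor readings. Even with the largest mock-up SD (4.39 mmHg) and zero bias, w would have to reach about 2.45 mmHg. Over 0.67 to 1.79 mmHg that example moves only from 74.5% to between 74.2% and 72.0%. Table 2 is also a mock-up that the normal model does not reproduce: it shows 16 of 17 (94.1%) within 5 mmHg at V06, and 89 of 101 (88.1%) over V02 to V06.

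**Conclusion.** The point holds as a low-cost improvement. The direction follows from the variance formula: for any w above zero, visit-mean limits are narrower than single-reading limits, and the share within 5 mmHg was higher for means in every case computed. The size is modest and uncertain, because w is not in the documents and the range 0.67 to 1.79 mmHg is an assumption. The share figures also assume normal differences, and all figures assume independent within-series errors and three readings per series. With only two readings averaged, half the reading-to-reading variance is removed instead of two thirds.

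On these assumptions the choice of unit can change the Protocol 9.5 verdict only near its boundary: a visit-mean share of at most about 72.3%, or visit-mean limits with a half-width above about 4.10 mmHg, both at the upper w. The documents do not support the inference that averaging is what would make the trial succeed. They do support saying that the planned limits should not be quoted for one home reading.

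**What to change.** In SAP 4.6.1:

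1. State which unit the Protocol 9.5 rule uses, both for the 70% share and for the ±5 mmHg limits.
2. Keep the visit-mean analysis. Beside it, report the limits of agreement and the share within 5 mmHg for a single ARGOS-SC reading against that visit's GAT mean. Use the first reading of each series. For the limits, the visit-mean variance plus two thirds of the within-series variance is an alternative when three readings were averaged.
3. Name the within-visit SD of the ARGOS-SC readings as the repeatability statistic. It replaces the assumed w above with an estimate.
4. Limit any agreement claim about home use to the single-reading result.

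Cost: a few lines of SAP text and code. The protocol already requires the three readings per series, so no new data are needed. The added figures will be slightly less favourable than the visit-mean ones.
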